LTA	Latent Transition Analysis
LPS	Lipopolysaccharide
MDM	Monocyte-derived Macrophages
MDT	Multi-Disciplinary Team
NHS	National Health Service
NICTU	Northern Ireland Clinical Trials Unit
NPV	Negative Predictive Value
PBW	Predictive Body Weight
PBMC	Peripheral Blood Mononuclear Cells
PEEP	Positive end-expiratory Pressure
PI	Principal Investigator
POC	Point of Care

QUB	Queen's University Belfast
REC	Research Ethics Committee
RR	Respiratory Rate
RMP	Registered Medical Practitioner
ROI	Republic of Ireland
SAP	Statistical Analysis Plan
SOFA	Sequential Organ Failure Assessment
SOP	Standard Operating Procedure
TMF	Trial Master File
TMG	Trial Management Group
SSC	Study Steering Committee
UK	United Kingdom
VFD	Ventilator Free Day

1. BACKGROUND AND DESIGN

Full details of the background to the study and its design are presented in the protocol.

The hypothesis that is under investigation is that patients prospectively classified to the hyper-inflammatory ARDS phenotype on the basis of clinical characteristics and a novel POC biomarker assay will have worse clinical outcomes than the hypo-inflammatory phenotype.

Aim:

The purpose of this project is to prospectively identify hyper- and hypo-inflammatory phenotypes in patients with ARDS and AHRF, and determine clinical outcomes associated with each phenotype.

Objectives:

Primary:

(i) Assess the clinical outcomes in patients with ARDS according to their prospectively defined inflammatory phenotype determined using a POC assay.

Secondary:

- (i) Assess the agreement of the phenotype allocation using a POC assay and latent class analysis (LCA) from biomarkers and the clinical study dataset
- (ii) Assess the stability of phenotype allocation over time
- (iii) Feasibility of delivering a POC assay in the NHS intensive care setting
- (iv) Identify if inflammatory phenotypes are present and influence outcomes in patients with AHRF

Patients will be eligible for the study if they meet the inclusion criteria.

Inclusion criteria

1. Patient is receiving mechanical ventilation, CPAP or high flow nasal oxygen (HFNO)
 2. a) ARDS as defined by the Berlin definition [6]
 - Onset within 1 week of identified insult
 - Within the same 24-hour time period:
 - i. Hypoxaemic respiratory failure ($\text{PaO}_2/\text{FiO}_2$ ratio $\leq 40\text{kPa}$ on $\text{PEEP} \geq 5\text{ cmH}_2\text{O}^*$)
 - ii. Bilateral infiltrates consistent with pulmonary oedema not explained by another pulmonary pathology
 - iii. Respiratory failure not fully explained by cardiac failure or fluid overload
- OR
- b) AHRF as defined by
 - Within the same 24-hour time period:
 - i. Hypoxaemic respiratory failure ($\text{PaO}_2/\text{FiO}_2$ ratio $\leq 40\text{kPa}$ on $\text{PEEP} \geq 5\text{ cmH}_2\text{O}^*$)

- ii. Unilateral infiltrates on chest imaging not fully explained by effusions, collapse, or nodules
- iii. Respiratory failure not fully explained by cardiac failure or fluid overload

The time of onset of ARDS is when the last ARDS criterion is met.

*PEEP assumed ≥ 5 cmH₂O if on HFNO

[figure not shown]
Patients will not be eligible for the study if they meet any of the exclusion criteria.

Exclusion criteria

1. Age <18 years of age
2. More than 72 hrs after onset of ARDS/AHRF
3. Receiving ECMO at the time of recruitment
4. Treatment withdrawal imminent within 24 hours
5. DNAR (Do Not Attempt Resuscitation) order (excluding advance directives) in place*
6. Declined consent
7. Prisoners

*Intended to only exclude patients who are not receiving active medical management and are receiving palliative care.

PHIND Schematic Diagram

2. OUTCOME MEASURES

2.1 Primary outcome measure(s)

The primary outcome is mortality at 60 days in the hyper-inflammatory and hypo-inflammatory phenotypes in patients with ARDS.

2.2 Secondary outcome measures

- (i) Difference in time to extubation, intubation rate in patients on HFNO, re-intubation rate, ventilator free days at day 28, duration of ventilation, length of intensive care unit (ICU) and hospital stay as well as 28-day mortality, in the hyper-inflammatory and hypo-inflammatory phenotypes.
- (ii) Agreement of phenotype classification using a POC assay and commercially-available assays
- (iii) Agreement of phenotype classification using a POC assay and LCA
- (iv) Agreement of phenotype classification between baseline and day 3
- (v) Feasibility of delivering a POC assay in NHS/HSE intensive care setting as measured by assay technical failure rate.

- (vi) Frequency of inflammatory phenotypes in patients with AHRF and difference in outcomes as described for ARDS phenotypes.

2.3 Study timeline

It is planned that the recruitment period will start in November 2019 and continue for at least 18 months. Following the completion of recruitment and follow-up, there will be a close out period.

2.4 End of study

For the purposes of submitting the end of study notification to the Sponsor and Research Ethics Committee (REC) the end of study will be considered to be when database lock occurs for the final analysis. The study will be stopped prematurely if:

- Mandated by the Research Ethics Committee (REC)
- Mandated by the Sponsor (e.g. following recommendations from the Study Steering Committee (SSC))
- Funding for the study ceases

The REC originally providing a favourable opinion of the study will be notified in writing once the study has been concluded or if terminated early

3. DATA

3.1 CRF Forms and variables

Full details of the data to be collected and the timing of data collection are described in the study protocol.

A copy of the CRFs is presented in the Trial Master File.

3.2 Management of datasets

Following the entry of patient data into the study database, the data will be processed as per the CTU SOPs. Data queries will be generated for site staff as required to clarify data or request missing information. The designated site staff will be required to respond to these queries within approximately 2 weeks. All queries will be responded to and resolved within the study database. Any amended information will then be entered in the study database.

The Data Manager in collaboration with the Study Statistician will extract data from MACRO following procedures as detailed in the SOP DM09 Database Closure/Lock and the corresponding study Data Management Plan (DMP).

3.3 Data completion schedule

The time points for completion of Case Report forms are reported in the table below.

CRF Page	Patient Recruitment and Eligibility	Day 0 (Baseline)	Day 1	Day 3	Day 7	Day 14	Day 28	Day 60	Event Driven
Recruitment									
Inclusion Criteria									
Exclusion Criteria									
COVID-19 Status									
Demographics									
Medical History									
ICNARC Case Mix Programme (CMP)									
ICU Admission									
Aetiology of ARDS AHRF									
Vital Signs									
Haematology									
Biochemistry									
Day 0 ABG									
Day 0 Ventilation Parameters and Adjunctive Therapies									
Murray Lung Injury Score									
Day 0 SOFA Score									
Day 0 SOFA Score Calculated									
Day 0 Additional Treatment									
Child Pugh Score									
Day 0 Research Samples									
Day 1 POC Assay									
Day 3 Vital Signs									
Day 3 Haematology									
Day 3 Biochemistry									
ABG									
Ventilation Parameters and Adjunctive Therapies									
ECHO									
SOFA Score									
SOFA Score Calculated									
Additional Treatment									
Overall Fluid Balance									
Day 3 Research Samples									
Day 3 POC Assay									
Ventilation History									
Death Report Form									
Transfer of Patients									
Development of ARDS									
Research Samples at discharge and post discharge									
Discharge									
Consent to Continue									
Withdrawal of Agreement/Consent									
Protocol Deviation									
Co Enrolment									
Additional Comments									
Investigator Statement									

3.4 Data verification

Study specific data validation checks will be implemented. The process of data validation ensuring the accuracy and quality of the data will be carried out according to SOP DM04 Data Validation and Discrepancy Management.

Data verification, consistency and range checks will have been performed at the data entry stage by the CTU, as well as checks for missing data (copies can be found in the TMF) according to SOP DM04. Additional range, consistency and missing data checks will be performed, as appropriate, when the analysis is performed (and when the datasets for analysis are constructed). All variables will be examined for unusual, outlying, unlabelled or inconsistent values.

Given the thorough nature of our follow-up procedure we expect the issue of missing data to be relatively minimal. We anticipate high compliance with initial data collection as this is close to the time of patient registration.

Any problems with study data will be queried with the Trial Managers, Data Managers, or statisticians, as appropriate. If possible, data queries will be resolved, although it is accepted that due to administrative reasons and data availability a small number of problems will continue to exist. This will be minimised.

Every effort will be made to minimise missing baseline and outcome data in this study. The level and pattern of the missing data in the baseline variables and outcomes will be established by forming appropriate tables and the likely causes of any missing data will be investigated. This information will be used to determine whether the level and type of missing data has the potential to introduce bias into the analysis results for the proposed statistical methods, or substantially reduce the precision of estimates related to treatment effects. If necessary, these issues will be dealt with using multiple imputation or Bayesian methods for missing data as appropriate.

3.5 Data coding

The variable codings will be as specified on the CRF.

4. DEFINITION OF TERMS

Data will be censored at 60 days for all outcomes from the date of last patient recruited.

Term	Definition
Unassisted breathing	No ventilatory support is defined as; extubated with supplemental oxygen or room air, or open T-tube breathing, or tracheostomy mask breathing, or CPAP without inspiratory pressure support for 48 hours. Patients receiving pressure support via non-invasive ventilation (except for sleep disordered breathing) or extra-corporeal lung support will be defined as receiving ventilatory support.
Discharge from critical care	First discharge to a ward in the hospital or another hospital; a transfer between ICUs is not considered a discharge from critical care. Hospital discharge is the first date that the patient is discharged to home/community, a transfer between hospitals is not considered as a hospital discharge.
Ventilator free days (VFDs) to day 28	
The number of days from the time of initiating unassisted breathing to day 28 after the date of commencing ventilatory support, assuming survival for at least 48 hours after initiating unassisted breathing and continued unassisted breathing to day 28. If the patient was receiving ventilatory support prior to ICU admission, the ICU admission date will be considered as the start of the VFD calculation. If a patient returns to assisted breathing and subsequently achieves unassisted breathing to day 28, VFDs will be counted from the end of the last period of assisted breathing to day 28. A period of assisted breathing lasting less than 24 hours and for the purpose of a surgical procedure will not count against the VFD calculation. If a patient was receiving assisted breathing at day 27 or dies prior to day 28, VFDs will be zero. Patients transferred to another hospital or other health care facility will be followed to day 28 to assess this endpoint.
 
The number of days alive and free from ventilation between final successful weaning and day 28 after study enrolment.
 $VFD = \begin{cases} (28 - x), & \text{if patient alive at day 28 and } x \leq 27 \\ 0, & \text{if patient requires mechanical ventilation for 28 days or more} \\ 0, & \text{if patient died within 28 days or } x > 27 \end{cases}$ 
Where x is number of days until patient achieved unassisted breathing

Duration of ventilation (days)	From the date of commencing ventilatory support, or the date of ICU admission, if the patient was receiving ventilatory support prior to ICU admission, to the time of initiating unassisted breathing.

	
Duration of ventilation
 
Date of unassisted breathing – Date of commencing ventilatory support, if the patient achieved unassisted breathing
 $= \begin{cases} \text{Date of death} - \text{Date of commencing ventilatory support, if the patient died prior to achieving unassisted breathing} \end{cases}$
Duration of ICU stay (days)	
Duration of critical care and hospital stay will be counted from ICU admission to discharge.
 
Duration of ICU stay
 
Date of first ICU discharge – Date of ICU admission, if the patient is alive at ICU discharge
 $= \begin{cases} \text{Date of death} - \text{Date of ICU admission, if the patient died prior to ICU discharge} \end{cases}$
Duration of hospital stay (days)	
Duration of critical care and hospital stay will be counted from ICU admission to discharge.
 
Duration of hospital stay
 
Date of first hospital discharge – Date of ICU admission, if the patient is alive at hospital discharge
 $= \begin{cases} \text{Date of death} - \text{Date of ICU admission, if the patient died prior to hospital discharge} \end{cases}$ 
Hospital discharge is the first date that the patient is discharged to home/community, a transfer between hospitals is not considered as a hospital discharge.

Extubation	First time being successfully free from an endotracheal tube or a tracheostomy tube for 48 hours
Time to extubation	From date of intubation to extubation, or from the date of ICU admission to successful extubation, if the patient was intubated prior to ICU admission.

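### Four duration outcomes start at ICU admission, start of ventilation or intubation rather than at enrolment, so the phenotype tests mix in time before the phenotype was measured and are biased if that time differs by phenotype

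*Supplement*

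**What the plan says.** All four definitions are in SAP section 4.

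- **Duration of ventilation** runs "From the date of commencing ventilatory support, or the date of ICU admission, if the patient was receiving ventilatory support prior to ICU admission", to unassisted breathing or death.
- **ICU and hospital stay:** "Duration of critical care and hospital stay will be counted from ICU admission to discharge".
- **Time to extubation:** "From date of intubation to extubation, or from the date of ICU admission to successful extubation", the second start applying when the patient was intubated before ICU.

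Entry is tied to a different clock. Section 1 requires respiratory support (mechanical ventilation, CPAP or HFNO) to be under way and excludes patients "More than 72 hrs after onset of ARDS/AHRF". It adds that "The time of onset of ARDS is when the last ARDS criterion is met". For ARDS only, onset must also fall within 1 week of the insult. Neither rule limits days in ICU or on a ventilator before enrolment.

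Sections 7.2 and 8.5 compare these outcomes between phenotypes by Mann-Whitney or t-tests. Section 8.5 adds adjusted models for time to extubation and duration of ventilation (age, co-morbidity, aetiology, vasopressor requirement, PF ratio). It gives none for ICU or hospital stay.

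**The concern.** The study asks whether a phenotype measured at day 0 goes with worse outcomes afterwards. Days in ICU or on a ventilator before day 0 cannot be a consequence of what was measured then. They depend on how and when respiratory failure arose, which may or may not be related to phenotype. If it is, the difference in pre-enrolment time is added to the difference in outcome and can create, hide or exaggerate a contrast.

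Time to extubation has a second fault. Patients on HFNO at entry can be intubated later, and their clock then starts after enrolment. Someone intubated on study day 10 and extubated on day 12 scores 12 − 10 = 2 days. Someone intubated at entry and extubated on day 5 scores 5. The first patient looks better although extubated a week later, and enters the comparison only through an event after baseline.

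**Working it through.** **1. How long can the pre-enrolment period be?** For ARDS, section 1 allows 7 days from insult to onset and 72 h (3 days) from onset to enrolment. A patient admitted to ICU and ventilated on the day of the insult can enter with 7 + 3 = 10 days already counted; a new insult in ICU allows more. AHRF has no insult-to-onset limit. A patient with ARDS at ICU admission may enter with a day or less.

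**2. Does anything in the plan remove or show these days?**

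| Place in SAP | What it does | Covers pre-enrolment time? |
|---|---|---|
| 7.3, samples within 24 h or 48 h | Limits ARDS diagnosis to sample | No limit from ICU admission or intubation to sample |
| 8.3, baseline characteristics | Lists items by phenotype | No days ventilated or in ICU before enrolment |
| 8.5, adjusted ventilation and extubation | Includes aetiology and co-morbidity | No timing term |
| 8.5, ICU and hospital stay | Mann-Whitney only | No adjustment |

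**3. Can the clock start after enrolment?** Yes. Section 4 classes "CPAP without inspiratory pressure support for 48 hours" as unassisted breathing, so a patient on plain CPAP at entry may begin ventilatory support later. The Appendix 1 tables list time to extubation for the HFNO cohort at 30 litres per minute or more, and for the non-invasive cohort under LCA allocation. If those cohorts are defined by support at entry, these figures come from patients intubated afterwards.

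**4. Size.** The SAP states no design figure for durations. Its only one is for mortality: 347 and 116 patients at 17% v 32%. I obtain 91.2% power (90% stated); 347/0.9 = 386 and 116/0.9 = 129, total 515. I use 347 and 116 as inputs. All gaps, durations and SDs below are assumptions.

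*Closed form.* With no true difference, a mean gap difference g and outcome SD s, the standard error is s × √(1/347 + 1/116) = 0.1073s. The rejection rate is Φ(g/SE − 1.96) + Φ(−g/SE − 1.96). For s = 10, g = 1: g/SE = 1/1.073 = 0.93, giving about 15%.

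| SD (days) | g = 0.5 | g = 1 | g = 2 | g = 3 |
|---|---|---|---|---|
| 6 | 12% | 34% | 88% | 100% |
| 8 | 9% | 21% | 65% | 94% |
| 10 | 8% | 15% | 46% | 80% |
| 14 | 6% | 10% | 27% | 52% |

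*Simulation.* Post-enrolment time is gamma (shape 1.5), the gap exponential, the test Mann-Whitney, deaths ignored. Gaps and means are hyper v hypo.

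| Mean post-enrolment days | Mean gap | p<0.05, enrolment origin | p<0.05, SAP origin |
|---|---|---|---|
| 10 v 10 | 2 v 2.5 | about 5% | about 9% |
| 10 v 10 | 2 v 3 | about 5% | 22–26% |
| 10 v 10 | 1.5 v 3.5 | about 5% | about 67% |
| 20 v 20 | 2 v 3 | about 5% | about 11% |
| 20 v 20 | 1.5 v 3.5 | about 5% | about 26% |
| 12 v 10 | 2.5 v 2.5 | 44% | 42% |
| 12 v 10 | 2 v 3 | about 44% | about 10% |
| 12 v 10 | 1.5 v 3.5 | 46% | 7% |

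In the last row the median difference moves from +1.6 to −0.5 days. In the row above it shrinks to about +0.6 and keeps its sign. A second model (lognormal durations, gamma gaps, mean 10 days, no true difference) gives 12%, 31% and 79% for gaps of 2 v 2.5, 2 v 3 and 2 v 4 days.

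**The case against.** Time from ICU admission is an explicit, reproducible measure of total burden, and these are secondary outcomes of an observational study whose primary outcome is 60-day mortality. That stands; it is why the totals should be kept as description and why the point carries no more weight than it does.

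The bias needs pre-enrolment time to differ by phenotype, and the SAP gives neither the times nor a direction. The simulated rows with unequal gaps put the longer gap in the hypo-inflammatory group; with the opposite gap, a true hyper-inflammatory excess would be exaggerated instead. Longer, more variable outcomes dilute the effect, as the 20-day rows show. The adjusted models for ventilation and extubation include aetiology and co-morbidity, which partly address how ARDS arose, though not when.

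Three stronger readings are tempting and not supported.

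- A reader might infer that every clock starts before enrolment. Some start later, as step 3 shows.
- A reader might infer that time to extubation always starts at intubation. ICU admission replaces an earlier intubation.
- A reader might picture a trauma patient who develops ARDS on ICU day 8. With trauma as the insult, the 1-week rule excludes that patient; a new insult in ICU would be needed. The rule limits insult to onset only, so it narrows the problem without removing it.

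**Conclusion.** The point holds as a conditional bias in four secondary outcomes. The definitions place time before the phenotype was measured inside the tested outcome for most patients, and use a post-enrolment origin for some others. Nothing in the plan corrects this or would let a reader see it.

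The documents do not support saying that the results will be false or reversed. With equal gaps the loss is about 2 percentage points of power (44% to 42%). With a half-day difference, false rejection is about 9% at a mean duration of 10 days. With a one-day difference it is 22–26% at a mean of 10 days and about 11% at a mean of 20. Reversal of a true 2-day excess in means appeared at a gap of 1.5 v 3.5 days, not at 2 v 3. These figures rest on assumed distributions and ignore deaths.

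The point concerns where the clock starts. How death ends these durations is a separate matter that a change of origin does not cure: with deaths of 17% v 32% and an assumed mean time to death of 7 days, a true 2-day excess shows as about 0.9 days under either origin when gaps are equal.

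**What to change.** For the between-phenotype tests, revise SAP section 4 as follows.

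1. Count duration of ventilation, ICU stay and hospital stay from day 0 (enrolment).
2. Restrict time to extubation to patients intubated at day 0, and count it from day 0.
3. Add days ventilated and days in ICU before enrolment to the baseline characteristics in section 8.3, by phenotype.
4. Keep totals from ICU admission as description, without a test.

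The Appendix 1 tables should follow, including removal of time to extubation from cohorts not intubated at entry.

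**Cost.** Definitions and tables change; no new data are needed. The present formulas do not use the enrolment date, but the study must hold it, and section 3.3 lists CRF pages for recruitment, ICU admission and ventilation history. The tested figures will no longer equal total burden. Patients intubated after entry leave time to extubation; those on HFNO at entry still count in the intubation-rate outcome.

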5. SAMPLE SIZE CALCULATIONS

Data from several retrospective analyses have shown that the percentage of patients with ARDS in the hyper-inflammatory sub-group was 27-34% of the overall population, that the mortality in the hypo-inflammatory sub-group was 17-23%, with a mortality difference between the hyper-inflammatory and hypo-inflammatory sub-groups ranging from 15-32%. A conservative percentage of patients in the hyper-inflammatory sub-group of 25%, a mortality in the hypo-inflammatory sub-group of 17% and a difference in 28-day mortality between the hyper-inflammatory and hypo-inflammatory sub-groups of 15% was assumed. The mortality in the hyper-inflammatory group is assumed to be 17% under the null hypothesis and 32% under the alternative hypothesis [7-10].

Based on a two group chi-square test, group sizes of 347 in the hypo-inflammatory group and 116 in the hyper-inflammatory group achieves 90% power at a two-sided significance level of 0.05 to detect a mortality difference between the groups of 15%. Based on our previous experience the group sizes

have been inflated by 10% to allow for technical failure, drop-out or loss to follow-up giving group sizes of 386 in the hypo-inflammatory group and 129 in the hyper-inflammatory group. As such, at least 515 patients with ARDS will be recruited.

An additional exploratory cohort of patients with COVID-19 will be recruited. No formal sample size calculation for this cohort is feasible. An indicative sample of up to 100 patients will be recruited in this cohort during the course of the study, however it is recognized that this is an estimate which will be dependent on the duration of the COVID-19 pandemic.

A further exploratory cohort of up to 300 patients with AHRF will be recruited. No formal sample size calculation for this cohort is feasible as these subphenotypes have not been described in such AHRF patients before. A sample of 300 patients is required in order to provide a minimum sample to undertake latent class analysis.

